[8] Scans are to be done at the end of 2 cycles (i.e., every 6 weeks; [1-3 days before next cycle begins]) for the first 6 cycles (18 weeks) and at end of 3 cycles (i.e., every 9 weeks; [1-3 days before next cycle begins]) thereafter, and at End of Treatment (EOT) visit by CT, PET/CT or MRI with contrast (per treating investigator's discretion) using the same method as at baseline. Tumor measurements will be done using RECIST v1.1. To be assigned a status of PR or CR, changes in tumor measurements must be confirmed by repeat assessments that should be performed 6 weeks after the criteria for response are first met. In the case of SD, measurements must have met the SD criteria at least once after study entry at a minimum interval of 6 weeks.

[9] Hemoglobin, Hematocrit (HCT), Red Blood Cells (RBC), White Blood Cells (WBC) with total and differential count, absolute lymphocyte count, absolute neutrophil count (ANC) and platelets.

[10] Serum Biochemistry will include:
Hepatic function indicators: total bilirubin, direct bilirubin, alkaline phosphatase, aspartate aminotransferase (AST)/SGOT, alanine aminotransferase (ALT)/SGPT, albumin and total protein.
Renal function indicators: blood urea nitrogen (BUN), creatinine
Electrolytes: sodium, potassium, chloride, calcium and bicarbonate
Other: glucose (random)

[11] Urine samples will be tested for pH, appearance, color, specific gravity, turbidity, ketones, bilirubin, blood, glucose, protein, nitrites, urobilinogen, and leukocyte esterases. Microscopic exam includes bacteria, cast, crystals, epithelial cells, RBC and WBC.

[12] Only performed on women of childbearing potential

[13] Blood sample collection for CTCs PD-L1/CCR5 analysis to be taken prior to the treatment administration at baseline (C1D1), on Day 1 (CXD1) of each subsequent cycle, and at the end of treatment (EOT).

[14] Blood sample collection for CTC and CAMLs analysis to be taken prior to treatment administration at baseline (C1D1), on Day 1 (CXD1) of each subsequent cycle, and at the end of treatment (EOT).

[15] Archival breast tissue (primary or metastatic site) will be collected from all patients at the pre-screening period and analyzed for presence of CCR5. Note: If no archival tissue is available, fresh biopsy to be done of the primary or metastatic site.

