4.4 FOLLOW-UP PERIOD

Duration of Follow Up

- An End of Treatment (EOT) visit will be conducted 30 (\pm 3) days after the last treatment visit (i.e., after last dose of leronlimab (PRO 140) and carboplatin).
- All patients will be followed for adverse events for 30 days after last dose of leronlimab (PRO 140) and Carboplatin, or until the patient starts a new treatment, whichever occurs first.
- Subjects who discontinue treatment for unacceptable adverse event(s) will be followed until resolution or stabilization of the adverse event (i.e. the grade is not changing).
- If a subject stops treatment due to unacceptable adverse event(s) but has not demonstrated disease progression, then the subject will be followed with imaging studies every 9 weeks until the time of progression radiographically according to RECIST v1.1 criteria. In the event that a radiographic response is detected, then this event will be included as a response in the final analysis, and the time of progression used in calculation of the survival analysis.
- Subjects will be followed up by clinic visits or phone call or another method of contact, for survival status every 3 months (\pm 1 month) for 2 years after treatment discontinuation or until death, whichever occurs first.

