4.4.1. End of Treatment Visit (EOT)

An EOT visit will take place 30 (\pm 3) days from the last treatment visit.

The following assessments will be performed at the EOT visit:

- Concomitant medications assessment (see [Section 7.5](#)),
- Review of Adverse Events (see [Section 9](#))
- Vital Signs (see [Section 7.6](#)),
- Physical examination, including evaluation of all body systems (see [Section 7.7](#)),
- ECOG Performance Status (see [Section 7.8](#)),

- 12-lead Electrocardiogram (see [Section 7.9](#)),
- Toxicity Assessment (see [Section 7.10](#)),
- Collection of lab specimens (see [Section 7.11](#)) for
 - Complete blood count
 - Biochemistry
 - Urine sample for urinalysis parameters
 - CTCs PD-L1/CCR5 Analysis
 - CTC and CAMLs Analysis
- Survival status (see [Section 7.16](#))

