7.9 ELECTROCARDIOGRAM (ECG)

A resting supine 12-lead ECG will be conducted at the Screening Visit (SV), at baseline (C1D1), and at End of Treatment (EOT) visit. A 12-lead EKG will be repeated during the study only if clinically indicated and at the discretion of the treating physician. The results will be evaluated by the Investigator. The following parameters will be recorded: ventricular rate (beats per minute), PR interval (msec), QRS interval (msec), QT interval (msec), and QTc interval (msec). Additionally, the Investigator will record the overall results of the ECG reading as either normal or abnormal, and as either not clinically significant or clinically significant. If abnormalities are observed, each will be recorded.

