8.7.3. Study Analyses

8.7.3.1 Primary Analysis

The primary analysis will be conducted on the Intent-to-treat (ITT) population.

Primary Outcome (Endpoints) Measures:

Phase Ib

- Maximum Tolerated Dose (MTD) by evaluation of dose-limiting toxicities (DLTs) of leronlimab (PRO 140) when combined with carboplatin AUC5.

Note: The MTD is defined as 1 dose level below the dose in which dose limiting toxicities (DLTs) were observed in ≥ 33% of the participants during Cycle 1.

Phase II

- Progression free survival (PFS) defined as time in months from the date of first study treatment to the date of disease progression or death from any cause, whichever comes first.

Note: All patients who receive at least one dose of leronlimab (PRO 140) and carboplatin combination will be included in the primary analyses of PFS. The Response Evaluation Criteria in Solid Tumors (RECIST v1.1) criteria will be used for objective tumor response assessment (when disease is measurable and non- measurable);

The time in months from start of treatment to progression or death will be measured for all patients who receive at least one dose of study drug. Patients will be followed up to 2 years after completion of treatment.

Secondary Outcome (Endpoints) Measures:

Phase Ib

- The number, frequency, and severity of adverse events (AEs) collected from the time of first treatment until 12 weeks after study treatment completion to evaluate safety of leronlimab (PRO 140) and carboplatin in subjects with CCR5+ mTNBC.

Note: Adverse events will follow National Cancer Institute Common Terminology Criteria for Adverse Events (CTCAE) version 5.0

Phase II

- PFS according to RECIST v1.1 in participants with Detectable Programmed Death-Ligand 1 (PD-L1)

Note: The PD-L1 expression testing will be performed at baseline. Breast tissue (primary or metastatic site) collected to analyze for the presence of CCR5 at pre-screening will additionally be used for evaluating PD-L1 expression levels.

- Overall response rate (ORR, defined as Complete Response (CR) + Partial Response (PR)), and clinical benefit rate (CBR, defined as CR + PR + Stable Disease (SD)) in subjects with CCR5+ mTNBC treated with leronlimab (PRO 140) and carboplatin.

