9.2 REPORTING AND FOLLOW-UP OF ADVERSE EVENTS

Report initiation for all AEs and serious adverse events (SAEs), (see [Section 9.3](#)), will begin at the time of the first treatment and continue up to the final study visit. All events will be followed to resolution or until 30 days after the subject completes the study. A final assessment of outcome will be made at that time.

All AEs must be recorded in the subject's medical records and on the CRF. AEs will be reported using customary medical terminology along with the following information: the onset and end dates, whether the event is considered to be a SAE (see [Section 9.3](#)), the impact the event had on study treatment (see [Section 9.2.1](#)), the CTCAE grade (intensity) of the event (see [Section 9.2.2](#)), the causality of the event (see [Section 9.2.3](#)), whether treatment was given as a result of the event (see [Section 9.2.4](#)), and the outcome of the event (see [Section 9.2.5](#)).

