8.3.3 Time to new metastases (TTNM)

Time to new metastases (TTNM) will be calculated using the formula in Section 7.9.3 and summarized descriptively. Kaplan-Meier analysis will be used to depict the median time (days) to new metastases.

Note: Recorded time from baseline metastatic disease (at time of enrollment) to the time of development of new metastasis in different site. New metastases in same site will be also recorded.

8.3.4 The change from baseline in circulating tumor cells (CTC) level in the peripheral blood The change from baseline in circulating tumor cells (CTC) level in the peripheral blood will be

calculated for each subject at each timepoint and summarized descriptively.

Note: Reported unit of measure will be the number of CTCs/milliliter. CTCs enumeration will be performed at baseline and at the time of response assessment. Fraction of baseline positive and change from ≥ 5 CTCs will be recorded and reported.

8.3.5 Overall survival defined as time in months from the date of first study treatment to the date of death

Overall survival defined as time in months from the date of first study treatment to the date of death will be presented using proportions and 95% confidence intervals.

Note: Patients will be followed from the start of treatment until 2 years post-treatment or death, whichever occurs first, and average survival time will be measured.

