8.4.3.2 Individual Patient Changes

Laboratory data will be classified into grades according to DAIDS toxicity grading. A severity grade of 0 will be assigned when the value is within normal limits.

The following summaries will be produced for the hematology and biochemistry laboratory data (by laboratory parameter):

- Shift tables using DAIDS grades to compare baseline to the worst post-baseline value will be produced for hematology and biochemistry laboratory parameters with DAIDS grades
- Shift tables using Low/High/Normal relative to the laboratory reference ranges to compare baseline to the worst post-baseline value will be produced for hematology and biochemistry laboratory parameters without DAIDS grades

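### End-of-treatment laboratory, vital-sign, ECG and CTC values can be taken after a new anticancer therapy has begun, and the SAP summaries have no cut-off that keeps them out

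*Protocol*

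**What the plan says.** **Visit timing.** Protocol 4.4.1 places the EOT visit 30 (±3) "days from the last treatment visit". The visit includes CBC, biochemistry, urinalysis, vital signs, a 12-lead ECG and both CTC blood samples. Neither 4.4, 4.4.1 nor Table 4-1 says what happens if another therapy has begun by then. Section 7.5.2 bars other anticancer therapy only in the Screening and Treatment Period, and Table 4-1 puts EOT in the Follow-up Period.

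**Adverse events.** Protocol 4.4 (also 7.10, Table 4-1 and the SAP's own schedule) follows events for 30 days after the last dose "or until the patient starts a new treatment, whichever occurs first". The endpoint definitions in protocol 8.7.3.1 and SAP 2.4.2 instead have events "collected from the time of first treatment until 12 weeks after study treatment completion". Protocol 9.2 gives a third rule: reporting "will begin at the time of the first treatment and continue up to the final study visit".

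**Analysis.** SAP 8.4.3.2 plans "Shift tables using DAIDS grades to compare baseline to the worst post-baseline value". SAP 8.4.4 counts patients with at least one abnormal vital sign after baseline, and SAP 8.4.5 applies its PR, QRS and ventricular-rate criteria to any assessment after baseline. SAP 8.3.4 has CTC change "calculated for each subject at each timepoint and summarized descriptively". SAP 7.1 defines baseline, but no section defines where the post-baseline period ends.

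**ECG schedule.** Under protocol 7.9, ECGs are done at screening, Cycle 1 Day 1 and EOT. Otherwise an ECG "will be repeated during the study only if clinically indicated and at the discretion of the treating physician".

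**The concern.** The protocol recognises that patients may move to another treatment inside the 30-day window, and the SAP recognises it for PFS by censoring before the new therapy. The descriptive safety tables and the CTC summary have no matching rule. A patient who progresses, starts the next regimen and then attends EOT contributes values that reflect that regimen, yet they are tabulated as post-baseline values of leronlimab plus carboplatin.

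Worst-value and any-value rules are sensitive to this, because one late value can set the patient's category. Scheduled on-study blood counts are taken on Day 1 of a cycle or up to 3 days before it, so an EOT sample drawn partway through a cycle of a new regimen could be the patient's lowest scheduled count. With no control arm, nothing in the tables would reveal the contamination. In Phase II, one patient placed in the wrong category moves a percentage by 1/30 = 3.3 points.

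**Working it through.** The documents give no figure on this point to reproduce. The Phase II size of 30 rests on clinical judgment, with no power calculation (SAP 3). The check is a comparison of rules, a calendar and an illustration.

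**1. Which outputs have a rule for new therapy?**

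| Output | Values used | Rule for new anticancer therapy |
|---|---|---|
| PFS (SAP 8.2.2) | First progression or death | Censored at last adequate scan before it |
| Laboratory shifts (SAP 8.4.3.2) | Worst after baseline | None |
| Laboratory change (SAP 8.4.3.1) | Each time point | None |
| Vital signs (SAP 8.4.4) | At least one abnormal value after baseline | None |
| ECG (SAP 8.4.5) | Any value, or at least one occurrence, after baseline | None |
| CTC (SAP 8.3.4) | Each time point, EOT included | None |
| TEAEs (SAP 8.4.1, protocol 8.7.3.2) | Onset on or after first treatment | None, and no end date |

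SAP 7.3 uses data as observed and SAP 7.4 rules out sensitivity analyses. A programmer following this text would include values taken after a switch.

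**2. Can a switch fall before EOT?** Inputs: leronlimab on Days 1, 8 and 15 of a 21-day cycle (protocol 4.3); scans 1–3 days before the next cycle (Table 4-1, footnote 8), which is cycle Day 19–21; EOT at 30 ± 3 days. With a last dose on Day 15 and visit windows ignored:

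- EOT day = 15 + 27 to 15 + 33 = Day 42 to 48.
- Shortest gap from scan to EOT = 42 − 21 = 21 days.
- Longest gap = 48 − 19 = 29 days.

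A patient whose progression is seen on a scheduled scan has three to four weeks before EOT, and 7.5.2 no longer bars other therapy once the Treatment Period has ended. A switch in that gap is possible.

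**3. How exposed is each measure?** Laboratory, vital-sign and CTC data are also collected during treatment, so EOT is one of several time points. For ECG it is the only scheduled post-baseline one. For a patient who has switched, all scheduled post-baseline ECG data come from after the switch.

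**4. Illustration of size.** The documents give neither the share switching before EOT (*f*) nor the chance that the new therapy creates a new worst category (*q*). I assume *f* = 10–50% and *q* = 10–40%.

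- EOT sample sets affected = 30*f*: 30 × 0.10 = 3; 30 × 0.50 = 15.
- Patients misclassified = 30*fq*: 30 × 0.10 × 0.10 = 0.3; 30 × 0.50 × 0.40 = 6, or 1–20% of 30.
- Chance of at least one = 1 − (1 − *fq*)^30: 1 − 0.99^30 = 26%; 1 − 0.80^30 = over 99%.

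**5. Are the adverse-event rules consistent?** No. One of the three windows stops at a new treatment, one runs 12 weeks past treatment completion and one runs to the final study visit. The TEAE definition has no end.

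**The case against.** The best case against the point runs as follows.

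- *The exception is missing, not denied.* No sentence says EOT samples must be taken after a new therapy has begun. Protocol 5 also asks that follow-up-visit data be recorded at premature discontinuation, which may bring some samples forward. That helps for withdrawals from the study. It is not tied to EOT, and a patient who stops treatment for progression and remains in survival follow-up has not clearly withdrawn: section 5 defines completion by that follow-up or death.
- *The data can be disentangled.* Laboratory results are listed by subject, medications carry start dates (7.5), and clinically significant abnormalities become adverse events with a causality rating. Shift tables assign no cause. This limits the harm, but the summary counts would still include the values.
- *Counts are not taken only at recovery.* Table 6-4 requires weekly CBCs during certain carboplatin holds, section 6.2.11 allows earlier checks, and unscheduled visits are recorded. So an on-study low may already be captured. This stands, and it is one reason misclassified patients would be fewer than affected sample sets.
- *The study is descriptive.* SAP 5 disclaims formal testing and SAP 8.4 plans no inferential safety statistics. This stands and keeps the point modest.

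Three stronger readings are tempting but unsupported. A reader might infer from 4.4 that the adverse-event tables stop at new therapy, so that laboratory and adverse-event tables must disagree. The TEAE definition has no such stop, and 4.4 is one of three conflicting windows. A reader might take 4.4.1 to count EOT from the last clinic visit when later injections are given at home. Protocol 4 and 4.4 and SAP 2.1 all explain the anchor as the last dose, so 4.4.1 is an incomplete restatement. A reader might also expect next-line therapy to flatter the whole CTC endpoint. Change is summarised by time point, so only the EOT row is exposed, and the direction is unknown.

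**Conclusion.** The point holds as a gap between the visit schedule and the analysis rules. EOT laboratory, vital-sign, ECG and CTC values may be taken on a new anticancer therapy, and the SAP gives no ground for leaving them out of the worst-value, any-value or EOT summaries. ECG is the most exposed measure.

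The size cannot be fixed from the documents. If 10–50% of patients switch before EOT, 3–15 of 30 Phase II sample sets are affected. If a further 10–40% of those acquire a new worst category from the new therapy, 0.3–6 patients are misclassified. Both ranges are assumptions. PFS is not affected, because it has its own censoring rule. This is an inexpensive improvement to descriptive tables and does not threaten the primary endpoint.

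**What to change.** **SAP 8.3.4 and 8.4.3 to 8.4.5.** Exclude from the change-from-baseline, worst-value and any-value summaries every laboratory, vital-sign, ECG or CTC value dated on or after the start of a new anticancer therapy, and list those values separately. No new data are needed: concomitant medications are recorded at EOT (4.4.1), later anticancer treatments at survival follow-up (4.4.2), and start dates under 7.5.

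**Protocol 4.4, 4.4.1 and Table 4-1.** Schedule the EOT assessments at 30 (±3) days after the last dose of study treatment or before the first dose of a new anticancer therapy, whichever comes first. Repeat the last-dose wording of 4.4 in 4.4.1, and state which last dose counts when the two drugs stop at different times, since the note to Table 6-4 lets leronlimab continue after carboplatin stops. This concerns when samples are taken, not when a patient may begin other treatment.

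**Adverse events.** Reconcile the three collection windows (4.4 and 7.10; 8.7.3.1 and SAP 2.4.2; 9.2) and give the TEAE definition an end date, so that adverse-event and laboratory tables use one window.

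**Cost.** A few sentences in each document. Some EOT visits will occur earlier. A patient who still switches before EOT loses those values from the summaries, including the only scheduled post-baseline ECG. The separate listing keeps them visible, and the earlier visit limits how often this happens.

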4.3 TREATMENT PERIOD

Subjects who meet all eligibility criteria, as per data gathered from Screening Period are to be treated. All subjects who fail to meet eligibility criteria will be considered screen failure and exit the study without further evaluation

Phase Ib

The dose finding portion of study will follow a “3+3” design. The maximum sample size for this portion of the study is 18 subjects that will be followed by treatment according to the schedule described above starting on Cycle 1, Day 1.

Phase II

The maximum sample size for this portion of the study is 30 subjects that will be followed by treatment according to the schedule described above starting on Cycle 1, Day 1.

During the Phase Ib and Phase II of the study, treatment may continue until one of the following criteria applies:

- Disease progression,
- Intercurrent illness that prevents further administration of treatment,
- Unacceptable adverse event(s), or
- Withdrawal of consent

Each treatment cycle consists of 21 days. Leronlimab (PRO 140) will be administered subcutaneously weekly on Days 1, 8, and 15 in combination with carboplatin AUC 5 on Day 1 of each cycle (every 21 days). Day 1 of Cycle 2 begins at Day 22.

4.3.1. Treatment Cycle 1, Day 1

The following assessments will be performed at the first treatment visit of Cycle 1:

- Concomitant medications assessment (see [Section 7.5](#)),
- Vital Signs and body weight measurement (see [Section 7.6](#)),
- Physical examination, including evaluation of all body systems (see [Section 7.7](#))
- ECOG Performance Status (see [Section 7.8](#))

- 12-lead Electrocardiogram (see [Section 7.9](#))
- Collection of lab specimens (see [Section 7.11](#)) for
 - Complete blood count
 - Biochemistry
 - Urine pregnancy test, for female subjects of childbearing potential.
 - Urine sample for urinalysis parameters
 - CTCs PD-L1/CCR5 analysis
 - CTC and CAMLs analysis

Note: Complete blood count, biochemistry and urinalysis can be performed within 3 days prior to each cycle start.

- Leronlimab (PRO 140) Administration (see [Section 6.1.3](#))
- Carboplatin Administration (see [Section 6.2.5](#))
- Post Injection Site Evaluation (performed by Investigator) (see [Section 7.13](#))
- Toxicity assessment (see [Section 7.10](#)) and Review of Adverse Events (see [Section 9](#))

4.3.2. Treatment Cycle 1, Day 8 & Day 15

The following assessments will be performed at during the remaining visits (Day 8 and 15) in the first treatment cycle:

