4.4.2. Survival Follow-up Visits

Survival follow-up visits will be performed every 3 months (± 1 month) for 2 years after treatment discontinuation or until death, whichever occurs first. Subjects will be followed up by clinic visits or phone call or another method of contact, for survival status. During the visit, the following assessments will be performed:

- Survival status
- Concomitant medications (limited to all subsequent anti-cancer treatments)
- Toxicity assessment

Note: Subjects who discontinue treatment for unacceptable adverse event(s) will be followed until resolution or stabilization of the adverse event (i.e. the grade is not changing).

- Tumor imaging assessment (see [Section 7.15](#) and note below)

Note: If a subject stops treatment due to unacceptable adverse event(s) but has not demonstrated disease progression, then the subject will be followed with imaging studies every 9 weeks until the time of progression radiographically according to RECIST v1.1 criteria. In the event that a radiographic response is detected, then this event will be included as a response in the final analysis, and the time of progression used in calculation of the survival analysis.

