5.1 REMOVAL OF SUBJECTS FROM STUDY TREATMENT AND/OR STUDY AS A WHOLE

Subjects can be taken off the study treatment and/or study as a whole at any time at their own request, or they may be withdrawn at the discretion of the investigator for safety, behavioral or administrative reasons. The reason(s) for discontinuation must be clearly documented on the appropriate eCRF and may include:

- Subject voluntarily withdraws from treatment (follow-up permitted)
- Subject withdraws consent (no follow-up permitted)
- Subject is unable to comply with protocol requirements
- Subject demonstrates disease progression
- Subject experiences unacceptable toxicity
- Treating physician determines that continuation on the study would not be in the subject's best interest
- Subject becomes pregnant
- Subject develops a second malignancy that requires treatment which would interfere with this study
- Subject becomes lost to follow-up (LTf)

If a subject fails to return for the scheduled study visit or is discontinued from the study, an attempt will be made to determine the reason(s). If the subject is unreachable by telephone, a registered letter will be sent to the subject requesting that he/she contact the clinic.

All patients with an ongoing SAE at the Post-Study (Follow-up) Visit (scheduled or premature) must be followed until the event is resolved (with or without sequelae) or deemed stable.

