8.2 Analysis Primary Outcome Measure

8.2.1 Maximum Tolerated Dose (MTD) by evaluation of dose-limiting toxicities (DLTs) of leronlimab (PRO 140) when combined with carboplatin AUC5

The MTD will be summarized descriptively. The proportion of subjects at the different MTD levels and those who were able to tolerate the highest dose of leronlimab will be summarized descriptively.

8.2.2 Progression free survival (PFS) defined as time in months from the date of first study treatment to the date of disease progression or death from any cause, whichever comes first.

PFS will be calculated from the date of initial dose to the date of objective disease progression or death due to any cause, whichever occurs earlier. If patients discontinued treatment due to toxicity, withdrew consent without disease progression or death, PFS will be censored at the date of the last evaluable tumor assessment. A patient with no evaluable tumor assessments or who drop out before first follow-up period will be censored at the date of informed consent. If two or more consecutively scheduled tumor assessments have no data (not evaluable due to incomplete assessment, not assessed, or missing) and are followed by a PD assessment or death, the PFS will be censored at the last evaluable tumor assessment date prior to the assessments with no data. Patients will be explicitly censored for PFS at last adequate tumor assessment prior to initiation of new anticancer treatment or radiation.

Patients who are off-treatment without objective PD and getting the subsequent new anticancer therapy before the data cut-off then PFS will be censored at the last adequate tumor assessment before the new anticancer treatment start, regardless of whether there was a PD or death after the start of the new anticancer treatment.

Progression free survival (PFS) will be estimated using Kaplan-Meier curves, and the median PFS will be read from this curve.

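### After the EOT scan, progression is tracked only in subjects who stopped for an adverse event, so the Phase II PFS may be biased

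*Protocol*

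**What the plan says.** Protocol 4.4 sets the trigger for imaging off treatment as "If a subject stops treatment due to unacceptable adverse event(s) but has not demonstrated disease progression". Anyone who meets it is scanned at 9-week intervals until RECIST progression. The section also says what the result is for: "the time of progression used in calculation of the survival analysis". Protocol 4.4.2 lists tumour imaging among the survival follow-up items, but its note carries the same restriction. So do Protocol 7.10, Table 4-1 footnote 23 and SAP Appendix 1 footnote 22.

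There are other ways to stop without progression. Protocol 4.3 names "Intercurrent illness that prevents further administration of treatment". Protocol 5.1 adds physician decision and inability to comply, and separates "Subject voluntarily withdraws from treatment (follow-up permitted" from a withdrawal of consent, after which no follow-up is allowed.

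Two things remain for every subject who stops and has not withdrawn consent. One is a scan at the EOT visit, 30 (±3) days after the last treatment visit (Protocol Section 3, 7.15, Table 4-1 footnote 8; SAP 2.1), although the Protocol 4.4.1 list of EOT assessments omits it. The other is survival contact every 3 months for 2 years, which may be by phone. Protocol 7.15 keeps scans going for all subjects when dosing is interrupted; it does not mention discontinuation.

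**The concern.** PFS is the Phase II primary endpoint. It will be reported as a single Kaplan-Meier median from 30 subjects with no control arm, next to a background figure of about 5 months. By imaging one group of stoppers to progression, the protocol accepts that leaving treatment should not end progression follow-up. It applies this to one stop reason only, and that reason is a classification made by the investigator: adverse event, intercurrent illness and physician decision can describe the same patient.

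If the other stoppers tend to be deteriorating, the progressions that go unseen are early ones, and the curve sits too high. SAP 7.4 plans no sensitivity analysis, so the report would not show it. A censoring rule can be amended before database lock, but progression dates that nobody collected may be impossible to recover.

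**Working it through.** **Step 1. Who has progression ascertained.**

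| Route off treatment, no progression yet | EOT scan | After EOT |
|---|---|---|
| Unacceptable adverse event | Yes | Imaging every 9 weeks to progression |
| Voluntary stop, physician decision, inability to comply, intercurrent illness not classed as an adverse event | Yes | No imaging; contacts record survival, later anticancer therapy and toxicity |
| Consent withdrawn | No follow-up permitted | None |

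**Step 2. What SAP 8.2.2 does with the second row.** A subject who starts new anticancer therapy is censored at the last adequate scan before it. For the rest there is no explicit rule. The nearest one begins "If two or more consecutively scheduled tumor assessments have no data", and nothing is scheduled for these subjects after EOT. If the lapsed scans count as missed, the subject is censored at the last scan even if she later dies. If they do not, a later death is the event, dated after any unseen progression.

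**Step 3. Size if stops come shortly before progression.** The plan has no figure to reproduce: SAP Section 3 gives no power calculation, SAP Section 5 gives no formal test, and no stopping rate is stated. Assumptions: exponential PFS with a true median of 5.0 months; a share f of 10, 20 or 30% stopping at a time uniform over 0–6 or 0–12 weeks before progression.

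- *Ceiling.* If a share f of events becomes censoring at the event time, the observed hazard is (1 − f) times the true one and the median is 5/(1 − f): 5/0.9 = 5.6, 5/0.8 = 6.25, 5/0.7 = 7.1 months.
- *EOT scan missed (simulation).* 5.5 / 6.1 / 6.8–7.0 months.
- *EOT scan done (simulation).* 5.1–5.3 / 5.3–5.6 / 5.5–5.9 months.

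Hand check of the last line: 30 days is 30/7 = 4.3 weeks, so the scan catches about 4.3/6 = 71% of these progressions in the 0–6 week case and 4.3/12 = 36% in the 0–12 week case. With 71% caught, the ceiling becomes 5/(1 − 0.29f) = 5.15, 5.31, 5.48, which matches the lower ends. With 36% caught it is 5/(1 − 0.64f) = 5.34, 5.73, 6.19. The simulated upper ends are lower, because the uncaught subjects are censored before their event time and because no stop can precede the first dose.

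**Step 4. Direction under other stopping patterns.** A second model uses the protocol's scan grid (weeks 6, 12, 18, then every 9 weeks) and an assumed median survival after progression of 5.5 months. With full imaging, 6-month PFS is 0.55. Entries are for about 10 / 20 / 30% stopping.

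| Who stops | No EOT scan, later deaths not counted | No EOT scan, deaths counted | EOT scan, deaths not counted | EOT scan, deaths counted |
|---|---|---|---|---|
| 0–8 weeks before progression | 0.576 / 0.607 / 0.641 | 0.575 / 0.601 / 0.625 | 0.556 / 0.560 / 0.565 | 0.554 / 0.557 / 0.562 |
| Unrelated to progression | 0.548 / 0.547 / 0.547 | 0.557 / 0.565 / 0.579 | 0.543 / 0.540 / 0.532 | 0.551 / 0.553 / 0.554 |
| Subjects doing well | 0.541 / 0.533 / 0.523 | 0.549 / 0.547 / 0.549 | 0.548 / 0.543 / 0.540 | 0.548 / 0.548 / 0.548 |

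The upward shift is clear when stopping precedes progression and the EOT scan is missed. Without that scan, counting later deaths also pushes PFS up when stopping is unrelated to progression. Elsewhere the shift is small or downward.

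**Step 5. Against sampling error.** At n = 30, with full imaging, the 5th–95th percentile range of the Kaplan-Meier median in the second model is 4.1–8.3 months.

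**The case against.** The strongest reply is the EOT scan. It is required whatever the stop reason, and it falls where it helps most, about a month after a stop that anticipates progression. A reader might infer that progression in these subjects is never looked for; the documents do not support that. This stands, and it removes most of the modelled shift. It is still one scan. It is missing from the site-facing list in Protocol 4.4.1, and progression found after new therapy has started is not counted under SAP 8.2.2.

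The affected group may also be small. Protocol 9.1 defines an adverse event broadly, so much intercurrent illness could qualify as one. The synopsis and Protocol Section 4 name only progression, toxicity and consent withdrawal as reasons to stop, and Protocol 5.1 also covers removal from the study as a whole. This narrows the group but does not empty it: a voluntary stop with follow-up permitted is clearly left out.

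A reader might infer that the primary analysis treats adverse-event stoppers correctly and the others wrongly. That contrast does not carry through cleanly. SAP 8.2.2 as worded also censors subjects who discontinue for toxicity at the last evaluable scan, whereas Protocol 4.4 uses their later progression time. The SAP sentence could be read as covering only those who never progress, but it does not say so.

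Finally, SAP Section 5 calls the study hypothesis-generating, and Step 5 shows that sampling error is larger than the likely shift. Protocol 5.3 also asks for every attempt at follow-up of withdrawn subjects. These points lower the severity. They do not supply a progression date.

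**Conclusion.** The gap is real on the text: after the EOT scan, progression is ascertained only in subjects who stopped for unacceptable adverse events. The Phase II PFS may be biased, upward if the other stops reflect deterioration; otherwise the main loss is precision.

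The stronger statement, that PFS is biased upward, is tempting but not supported. The documents give neither a rate of such stops nor a link to prognosis, and Step 4 shows patterns with almost no shift or a downward one.

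Under the assumptions of Step 3, a true 5.0-month median reads 0.1–0.3, 0.3–0.6 or 0.5–0.9 months too long at 10, 20 or 30% stopping with the EOT scan done, and up to 0.5, 1.1 or 2.0 months too long if it is missed. SHOULD-FIX: the likely effect is modest, but it falls on the primary endpoint and can be reduced cheaply while data are still being collected.

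**What to change.** 1. **Protocol 4.4.2.** At each 3-monthly contact, for every subject who stopped without progression and has not withdrawn consent, collect routine-care scan reports and the date of any documented progression. State in the SAP that these count in PFS.
2. **Protocol 4.4.1.** Add the tumour scan to the EOT list, to match Protocol 7.15 and Table 4-1 footnote 8.
3. **SAP 8.2.2.** State how subjects who stop without progression and start no new therapy are handled, including whether unscheduled scans can count as missed and how a later death is treated. Reconcile the censoring of toxicity stoppers with Protocol 4.4.

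Extending the 9-weekly imaging to these subjects, where clinically appropriate, is optional. It adds procedures and would need thought for some stop reasons, such as pregnancy.

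Cost: a short protocol and SAP amendment and a little extra data entry, with no new procedures in the core fix. The drawback is that routine-care progression dates will not follow the protocol scan schedule.
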